4 INTRODUCTION

4.1 STUDY RATIONALE

Contrast-enhanced (CE) Magnetic Resonance Imaging (MRI) is a vital tool in diagnostic medicine. RVP-001 is being developed as a gadolinium (Gd)-free alternative to currently available general purpose MRI contrast agents, all of which belong to a class of compounds known as gadolinium-based contrast agents (GBCAs). General purpose MRI contrast agents are non-specific in their biodistribution and distribute in the blood pool and in the extracellular fluid (Aime & Caravan 2009). They are essential for routine diagnostic purposes and are used to help detect and stage a wide range of diseases, as well as to monitor disease progression and response to treatment (Klein et al. 2018). However, serious but rare side effects can occur with GBCAs, limiting their use. The United States (U.S.) Food and Drug Administration (FDA) advises that all GBCAs increase the risk for nephrogenic systemic fibrosis (NSF) among patients with impaired renal elimination of the drugs and requires a 'black box warning" directing physicians to avoid the use of GBCAs in these patients if possible; FDA later required other label updates to minimize the risk of NSF (FDA Drug Safety Communication 2010). Safety concerns continue to emerge as more becomes known about the long-term effects of GBCAs. It is established that residual Gd, in some chemical form, is retained in the brain and body for long periods (years) after administration of GBCAs; FDA has reacted with additional warnings required on drug labels (FDA Drug Safety Communication 2018). The indispensable role of GBCAs is reflected in the fact that they are administered over 8 million times per year in the U.S. (FDA MIDACM 2017).

Manganese (Mn), unlike Gadolinium, is a normal elemental component of the human body. Therefore, RVP-001 was designed to act in a functionally similar manner to GBCAs but to contain the biocompatible essential trace element Mn and not contain the gadolinium ion.

This highlights the high unmet medical need for a Gd-free alternative that can be used to provide important CE diagnostic MRI scans. Instead of Gd, RVP-001 utilizes chelated manganese ion (Mn²⁺) to produce contrast in MRI scans. By avoiding Gd altogether in the contrast agent, safety concerns based upon Gd would be precluded.

The goal of this first clinical trial, RVL--22, is to evaluate the safety, tolerability, pharmacokinetics, and elimination of single ascending doses (SADs) of RVP-001 when injected as a single intravenous (IV) bolus administration in normal, healthy adults.

4.2 BACKGROUND

RVP-001 is a low molecular weight chelate of Mn²⁺ that was designed and developed to provide a Gd-free alternative to GBCAs for IV use in CE MRI. RVP-001, also known in the scientific literature as Mn-PyC3A, comprises a rationally designed hydrophilic, anionic hexadentate chelator complexed to divalent manganese (Mn²⁺). This results in a chelate that simultaneously provides high relaxivity, is largely

confined to the extracellular space, and is highly resistant to Mn dissociation (Gale et al. 2018, Erstad et al. 2019).

The mechanism of action of MRI contrast agents is to reduce the relaxation times, T₁ and T₂, of water molecules in tissue. For example, in T₁-weighted MR images, tissue that has a shorter T₁ value has higher signal and appears brighter compared to tissue that has a longer T₁. Paramagnetic species such as Gd³⁺ (in GBCAs) or Mn²⁺ strongly reduce the T₁ of water molecules in close proximity to the metal ion, and as a result increase the MRI signal in a T₁-weighted image. The extent to which a contrast agent can change the relaxation time is characterized by its relaxivity and is denoted r₁ or r₂ depending on whether it refers to changing the T₁ time or T₂ time. Relaxivity is an inherent property of the contrast agent. Contrast agents with a higher r₁ relaxivity will cause a larger T₁ change at a given concentration than a contrast agent with a lower relaxivity. The amount of signal change generated by a contrast agent is proportional to both its relaxivity and its concentration within an anatomical region. The presence or absence of signal enhancement is used by physicians to identify whether pathology is absent or present (Klein et al. 2018). The most widely used indication for MRI contrast agents is for the detection of central nervous system (CNS) lesions. For example, many primary and metastatic brain tumors cause disruption of the bloodbrain barrier, resulting in concentration of the contrast agent within the lesion bed. This results in local enhancement making the tumor highly conspicuous on MRI scans (Klein et al. 2018).

The MR contrast effects of an Mn²⁺ based contrast agent are exemplified in the experience with mangafodipir trisodium (Mn-DPDP; Teslascan°), an agent that was FDA-approved for use in contrast enhanced hepatobiliary MR imaging. In humans and animals, Mn-DPDP dissociates in the body immediately after IV administration, with about 80% of the administered Mn being released from its chelator in humans (Toft et al. 1997), whereas RVP-001 was designed and has been demonstrated to remain intact and to be excreted intact. This strong Mn²⁺ chelating property of RVP-001 versus Mn-DPDP is reflected in conditional stability constants for the 2 compounds at pH 7.4: RVP-001 utilizes a chelator that has over 100,000 times higher affinity to Mn²⁺ than Mn-DPDP (Gale et al. 2015). This lower stability of Mn-DPDP leads to greater Mn²⁺ release and consequently to greater retention of injected Mn in the body, with 15% of the injected Mn from Mn-DPDP remaining in rats 5 days after IV administration (Grant et al. 1994) compared to 0.058 ± 0.051% of Mn from IV injected RVP-001 remaining in rats at 7 days after injection (Erstad et al. 2019). Unlike Mn-DPDP which dissociates upon injection, RVP-001 was designed to be chemically stable and not release free Mn²⁺ ion in the body. Bioanalytical studies showed that RVP-001 is rapidly eliminated intact without undergoing metabolism or degradation in rats, mice, and monkeys.

4.2.1 NON-CLINICAL STUDIES

Nonclinical pharmacology data indicate that RVP-001 is a unique, effective imaging agent based on MRI studies in mice and baboons. The effectiveness of RVP-001 in these studies was generally equivalent to that of comparator GBCAs. The acute safety of RVP-001 was assessed in a standard Good Laboratory Practices (GLP)-compliant battery of safety pharmacology studies of CNS, respiratory, and CV function. RVP-001 is the N-methyl-D-glucamine (meglumine) salt of the Mn complex. Some early studies used the sodium salt form which is denoted RVP-001-30.

RVL-101-22 Reveal Pharmaceuticals

Phase 1a Clinical Study Protocol

In nonclinical studies RVP-001 was shown to be chemically stable with a relaxivity comparable to GBCAs, and to provide effective contrast enhancement in animal models. RVP-001 has the desired pharmacokinetic (PK) attributes of rapid elimination, low tissue retention and resistance to metabolic degradation (Gale at al. 2015, Gale at al. 2018, Erstad et al. 2019, Zhou et al. 2021). RVP-001 was shown to undergo mixed hepatobiliary and renal elimination in mice, baboons, and rats (Gale at al. 2018, Erstad et al. 2019, Zhou et al. 2021), with increased fractional hepatobiliary elimination in a rat model of renal impairment (Zhou et al. 2021).

| _ |
|---|
| |
| |
| _ |
| |
| |
| |
| |
| |
| |
| |
| |
| |

Refer to the Investigator Brochure for details of all non-clinical studies to date. The proposed Phase 1a study will constitute the first in human (FIH) study of RVP-001 to assess safety and PK using a randomized SAD scheme.

4.3 RISK/BENEFIT ASSESSMENT

4.3.1 RISK ASSESSMENT

RVP-001 has not yet been evaluated in humans.

| In nonclinical toxicology studies in rats (Studies 1737-19008 and GD64LN) and cynomolgus monkeys |
|--------------------------------------------------------------------------------------------------------|
| (Studies 1737-19021 and MJ95QX), RVP-001 was found to be safe and well tolerated at projected clinical |
| useful doses. |
| |
| |
| |
| |
| |
| |
| |
| |
| |
| |
| |
| |
| |
| |
| |
| |
| |

4.3.2 KNOWN POTENTIAL BENEFITS

As the study treatment is not being given to subjects to treat any symptoms or illness, there will be no direct medical benefit from participation in this trial.

4.3.3 ASSESSMENT OF POTENTIAL RISKS AND BENEFITS

Mn has a well understood toxicity profile. Known effects from Mn toxicity inform potential safety concerns for the entire class of Mn-containing MRI contrast agents include the possibilities of Mn retention in the brain subsequent to chronic overexposure, hypersensitivity reactions, lowering of seizure threshold, and transient changes in CV function as a consequence of acute overexposure to free Mn2+. To mitigate risk from Mn exposure, RVP-001 was designed to stably chelate Mn2+, to remain intact while in the body, and to be excreted intact. Nonetheless FDA has requested Reveal submit expedited IND safety reports for any reports of seizure, stroke, cerebral venous thrombosis, QTc >480 msec, or QTc increase of 60 msec over baseline, regardless of assessment of causality.

More detailed information about the known and expected benefits and risks and reasonably expected adverse events (AEs) of RVP-001 may be found in the investigator's brochure (IB).

4.4 STUDY OBJECTIVES

The objectives of this study are as follows:

Primary objective:

To evaluate the safety and tolerability of SADs of RVP-001 in healthy adult volunteers.

Secondary objective:

To determine the pharmacokinetics and elimination of RVP-001 in healthy adult volunteers.

4.5 STUDY ENDPOINTS

Safety:

Safety will be evaluated throughout the study by assessing the following parameters: AEs, physical examinations, injection site monitoring, ECGs, vital signs, clinical laboratory evaluations, medical history, and prior and concomitant medications.

Pharmacokinetics and Elimination:

Plasma and urine will be analyzed by liquid chromatography with tandem mass spectrometry (LC-MS/MS) to measure the concentration of intact RVP-001 and to assess plasma pharmacokinetics. Urine and feces will be analyzed by inductively coupled plasma mass spectrometry (ICP-MS) for total Mn content to quantify elimination of injected Mn via the urine and feces. Additional assessments of biotransformation products may be performed.

5 STUDY DESIGN

5.1 OVERALL DESIGN

| This is a Phase 1a, single center, randomized, double-blinded, SAD-cohort study to assess the safety, |
|-------------------------------------------------------------------------------------------------------|
| tolerability, pharmacokinetics, and elimination of RVP-001 at four doses: |
| |
| |
| |
| |

During Phase 1a, no medical imaging will be performed.

Subjects will be confined to the Phase 1 facility from 24 hours prior to dose administration (Day -1) until 120 hours (Day 6) following dose administration. The plan is to enroll 4 dose cohorts of 8 healthy volunteers each, with two subjects receiving placebo and six subjects receiving RVP-001. For all cohorts, a staggered dosing schedule will include 2 sentinel subjects (1 active, 1 placebo) dosed initially, with remaining 6 subjects dosed at least 24 hours later.

If this initial dose is safe and well tolerated, as defined in the criteria to proceed to the next dose level, then the second dose cohort group will be administered. This cycle will proceed as described to each successive dose level.

Depending on safety and tolerability as well as on available PK data up to Day 6 (120 hours), the escalation scheme may be modified such that another intermediate dose level or a repeat dose is administered. This additional cohort will be optional and may be added depending on the outcome of the safety, tolerability, and PK assessments in the previous cohorts.

[figure not shown]
Subjects who withdraw or are withdrawn from the study after dosing for reasons other than safety and tolerability may be replaced after consultation between the Safety Committee members. In such case, the total number of subjects dosed will remain within a maximum of 10 subjects per cohort. Subjects withdrawn due to a study drug-related AE will not be replaced.

The dose escalation schema is shown in Figure 1.

RVL-101-22 Reveal Pharmaceuticals

Phase 1a Clinical Study Protocol

Figure 1 Dose Escalation Schema

5.2 JUSTIFICATION FOR DOSE

Phase 1a will be an escalating single-dose, safety, tolerance, and pharmacokinetic study of RVP-001 in dose cohort groups of healthy adult male and female volunteers (Table 1). The starting clinical dose is based on nonclinical safety, toxicity, and pharmacokinetic data, in accordance with FDA guidance (Guidance for Industry Estimating the Maximum Safe Starting Dose in Initial Clinical Trials for Therapeutics in Adult Healthy Volunteers, FDA 2005) and in conjunction with preclinical imaging data generated with

[figure not shown]

Table 1 Phase 1a Planned Dose Escalation

| Cohort | Dose (mg Mn/kg) | Number of Subjects (drug + placebo) | Process (sentinel +remaining) | Route of Administration |
|--------|--------------------|----------------------------------------|----------------------------------|----------------------------|
| 1a.1 | 2.0 | 6+2 | 2+6 | IV injection |
| 1a.2 | 4.0 | 6+2 | 2+6 | IV injection |
| 1a.3 | 7.0 | 6+2 | 2+6 | IV injection |
| 1a.4 | 12.0 | 6+2 | 2+6 | IV injection |
| 1a.5 | TBD | 6+2 | 2+6 | IV injection |

IV = intravenous; TBD = to be determined

5.3 END OF STUDY DEFINITION

A participant is considered to have completed the study if he or she has completed all phases of the study including the last visit or the last scheduled procedure shown in the Schedule of Activities (SoA), Section 3.2.

The end of the study is defined as completion of the last visit or procedure shown in the SoA in the trial for the last participant enrolled in the study.

6 STUDY POPULATION

6.1 JUSTIFICATION FOR THE STUDY POPULATION

This is a FIH study. A healthy volunteer population has been selected for the study because healthy subjects with no concomitant diseases and using no concomitant medications represent a homogeneous population allowing for proper evaluation of the safety, tolerability, and PK of a drug without confounding factors.

Since the risk to the developing human fetus following exposure to RVP-001 is unknown at this time, female subjects will be enrolled in this trial only if they meet all inclusion criteria and none of the exclusion criteria. To ensure that female subjects are not pregnant or likely to become pregnant during the study, confirmation will be obtained by serum and urine tests prior to study drug administration. In addition, female subjects of childbearing potential and non-surgically sterile male subjects will be required to use effective contraceptive methods for an appropriate duration (refer to Section 6.5 for acceptable contraceptive methods)

6.2 SAMPLE SIZE

Thirty-two (32) subjects (+ 8 subjects for potential replacement if applicable) will be enrolled in this study in 4 dose cohorts of 8 subjects each (6 RVP-001, 2 placebo).

Depending on safety and tolerability as well as on available PK data, the escalation scheme may be modified such that an additional intermediate dose level or a repeat dose is administered. This additional cohort will be optional and may be added depending on the outcome of the safety, tolerability, and PK assessments in the previous cohorts.

Subjects who withdraw or are withdrawn from the study after dosing for reasons other than safety and tolerability may be replaced after consultation between the Safety Committee members. In such case, the total number of subjects dosed will remain within a maximum of 10 subjects per cohort. Subjects withdrawn due to a study drug-related AE will not be replaced.

A sample size of 8 subjects per cohort randomized in a 3:1 ratio to the study drug vs placebo represents a typical panel for a first-in-human study. That number of subjects is judged adequate to achieve the study objectives.

6.3 INCLUSION CRITERIA

Subjects enrolled in this study will be from the community at large. The recruitment advertisements may use various media types (e.g., radio, newspaper, Clinical Research Organization [CRO] Web site, CRO volunteer database).

Subjects must meet all of the following criteria to be included in the study:

- 1) Healthy adults
- 2) Non-smoker (no use of tobacco products, e-cigarettes or nicotine replacement products within 12 months prior to screening)
- 3) \geq 18 and \leq 55 years of age at the time of signing informed consent
- Body Mass Index (BMI) > 18.0 and < 32.0 kg/m² at screening
- Body weight ≥ 55.0 kg for males and females at screening
- 6) Subject must be in good general health condition (i.e., full physical examinations, medical history, vital signs, 12-lead ECG, and clinical laboratory tests performed at screening) as determined by the investigator. Normal ECG is defined as normal cardiac conduction parameters including resting HR between 50 and 100 bpm, Fridericia-corrected QT interval (QTcF) ≤ 450 ms, and QRS interval < 120 ms

- 7) Subject shows normal biochemistry test results (within normal range or considered not clinically significant by the clinical investigator) at screening or admission including items listed below:
 - a. Blood urea nitrogen (BUN), and creatinine
 - b. Albumin and total protein
 - Alkaline phosphatase, Alanine Aminotransferase (ALT), Aspartate Aminotransferase (AST), and total bilirubin
 - d. Human immunodeficiency virus (HIV), Antibody HBsAg (anti-HBsAg) and antibodies against Hepatitis C virus (HCV) (anti-HCV)
- 8) Subject shows normal hematology test results (within normal range or considered not clinically significant by the clinical investigator) at screening or admission including items listed below:
 - e. Red blood cell (RBC) count
 - f. White blood cell (WBC) count with differential
 - g. Hemoglobin and hematocrit
 - h. Platelet count
- 9) Subject shows normal urinalysis test results (within normal range or considered not clinically significant by the clinical investigator) at screening or admission including items listed below:
 - a) pH and specific gravity (refer to Section 9.2)
 - b) blood, leukocyte, glucose, protein, ketones, and nitrite
 - c) Drug and alcohol abuse screening test (drugs of abuse are listed in Section 9.1.5)
- 10) Subject shows normal coagulation test results (within normal range or considered not clinically significant by the clinical investigator) at screening or admission, including prothrombin time (Pt), International Normalized Ratio (INR), and activated partial thromboplastin time (APTT).
- 11) Subject must agree to use an adequate method of contraception (as defined in Section 6.5)
- 12) Subject must be able to understand a written informed consent, which must be obtained prior to initiation of study procedures
- 13) Subject must be willing and able to comply with all study requirements

6.4 EXCLUSION CRITERIA

Subjects to whom any of the following applies will be excluded from the study:

- 1) Any clinically significant abnormality or abnormal laboratory test results found during medical screening; positive test for hepatitis B, hepatitis C, or HIV found during medical screening
- 2) History of clinically significant CV, renal, hepatic, chronic respiratory or gastrointestinal disease (except cholecystectomy); neurological or psychiatric disorder, as judged by the investigator
- Evidence of clinically significant hepatic impairment at screening and admission including any of:
 - a) Albumin above 1.3 × the upper limit of normal (ULN) or below 0.7 x the lower limit of normal (LLN)
 - b) ALT above 1.5 × ULN
 - c) AST above 2.5 × ULN
 - d) total bilirubin above 2.0 × ULN (total bilirubin accepted up to 2 × ULN if direct bilirubin is within normal limits)
- 4) Evidence of clinically significant renal impairment at screening including estimated Glomerular filtration rate (eGFR) of <60 mL/min or creatinine greater than 1.5 mg/dL. (The eGFR calculations will be performed using the CKD-EPI 2021 Refit Equation)
- Clinically significant cardiac findings at screening or admission including resting HR below 50 or above 100 bpm, or ECG abnormality or QTcF over 450 ms
- 6) Known allergies to any component of RVP-001
- 7) Known drug allergies or sensitivities which have resulted in Emergency Room visits, hospitalizations, or need to carry rescue Epipens as a matter of routine practice; moderate or severe allergies to any IV contrast agents; seasonal allergies requiring medication
- 8) History of asthma
- Subjects who have taken strong CYP inhibitors 14 days prior to first dose of study A list of these inhibitors is provided in Section 11.4 CYP Inhibitors (FDA Table of Substrates, Inhibitors, and Inducers 2020).
- 10) Subjects with diets that are high in Mn content (>2.5 mg/day). Foods known with high Mn content include shellfish (i.e., mussels, clams, oysters), hazelnuts, pecans, blueberries, pineapple, and/or supplements containing Mn
- 11) Vital sign abnormalities at screening or admission (systolic BP lower than 90 or over 140 mmHg, diastolic BP lower than 50 or over 90 mmHg)
- 12) History of significant alcohol abuse within two years prior to screening
 - a) or regular use of alcohol within six months prior to the screening visit (in males over 21 units per week and females over 14 units per week [1 unit = 12 oz 1 bottle/can of beer, 1 oz 40% spirit, or 5 oz glass of wine])
 - b) or a confirmed positive alcohol urine test at screening or admission
- 13) History of significant drug abuse or use of soft drugs or hard drugs (drugs of abuse are listed in Section Drug, Alcohol and Cotinine Screen 9.1.5) within 1 year prior to screening
- 14) A confirmed positive urine cotinine test at screening or admission.

- 15) Subjects who have received any investigational product (IP) in a clinical research study within 5 halflives or within 30 days prior to first dose. However, in no event shall the time between last receipt of IP and first dose be less than 30 days.
- 16) Use of medication other than topical products without significant systemic absorption:
 - a) prescription medication within 14 days prior to (the first) dosing
 - b) over-the-counter products including natural health products (e.g., food supplements and herbal supplements) within 14 days prior to (the first) dosing, with the exception of the occasional use of acetaminophen (up to 2 g daily)
 - c) a depot injection or an implant of any drug (including contraception) within 3 months prior to (the first) dosing
 - d) Coronavirus Disease 2019 (COVID-19) vaccines are accepted concomitant medications
- 17) Donation of plasma within 7 days prior to dosing; donation or loss of blood (excluding volume drawn at screening) of 50 mL to 499 mL of blood within 30 days, or more than 499 mL within 56 days prior to the first dosing
- 18) Positive highly sensitive pregnancy test at screening or admission for WOCBP.
- 19) Have poor venous access that limits phlebotomy at screening and admission
- 20) Evidence of current severe acute respiratory syndrome coronavirus 2 (SARS-CoV-2; the virus that causes COVID-19) infection
- 21) Male subjects with pregnant or lactating partners
- 22) Subjects who are, or are immediate family members of, a study site or sponsor employee
- 23) Any reason which, in the opinion of the Principal Investigator, would prevent the subject from participating in the study.

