 - c) a depot injection or an implant of any drug (including contraception) within 3 months prior to (the first) dosing
 - d) Coronavirus Disease 2019 (COVID-19) vaccines are accepted concomitant medications.
- 17) Donation of plasma within 7 days prior to dosing. Donation or loss of blood (excluding volume drawn at screening) of 50 mL to 499 mL of blood within 30 days, or more than 499 mL within 56 days prior to the first dosing.

- 18) Positive highly sensitive pregnancy test at screening or at admission for women of childbearing potential (WOCBP).
- 19) Have poor venous access that limits phlebotomy at screening and admission
- 20) Evidence of current severe acute respiratory syndrome coronavirus 2 (SARS-CoV-2; the virus that causes COVID-19) infection
- 21) Male subjects with pregnant or lactating partners
- 22) Subjects who are, or are immediate family members of, a study site or sponsor employee
- 23) Any reason which, in the opinion of the Principal Investigator, would prevent the subject from participating in the study.

Phase:

1a

Study Population: Heathy adult male and female volunteers will be enrolled in this study.

Number of subjects

Thirty-two (32) subjects (+ 8 subjects for potential replacement if applicable) will be enrolled in this study in 4 dose cohorts of 8 subjects each (6 RVP-001, 2 placebo per cohort).

Depending on safety and tolerability as well as on available PK data, the escalation scheme may be modified such that an additional intermediate dose level or a repeat dose is administered. This additional cohort will be optional and may be added depending on the outcome of the safety, tolerability, and PK assessments in the previous cohorts.

Subjects who withdraw or are withdrawn from the study after dosing for reasons other than safety and tolerability may be replaced after consultation between the Safety Committee members. In such case, the total number of subjects dosed will remain within a maximum of 10 subjects per cohort. Subjects withdrawn due to a study drug-related AE will not be replaced.

A sample size of 8 subjects per cohort randomized in a 3:1 ratio to the study drug vs placebo represents a typical panel for a first-in-human study. This number of subjects is judged adequate to achieve the study objectives.

Description of Sites/Facilities Enrolling Participants:

This study will be conducted at a single site.

Study Drug, Dose, and Mode of Administration:

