9.1.6 PREGNANCY TEST

A highly sensitive urine pregnancy test will be performed at screening for all female subjects. For WOCBP, a highly sensitive urine pregnancy test will also be performed before discharge. A highly sensitive serum pregnancy test will be performed at admission. The samples will be collected and processed as detailed in the clinical sample processing manual (CSPM).

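### Lactation excludes a man through his partner, but the protocol does not address a female subject who is herself breastfeeding

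*Combined protocol and SAP*

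**What the plan says.** The trial is open to both sexes (Section 3.1: "Heathy adult male and female volunteers will be enrolled in this study"), aged 18 to 55 and weighing at least 55 kg. Section 6.1 makes women's participation depend on the listed criteria: "female subjects will be enrolled in this trial only if they meet all inclusion criteria and none of the exclusion criteria". It then gives the aim of the female safeguards: "To ensure that female subjects are not pregnant or likely to become pregnant during the study".

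Two exclusion criteria carry the reproductive restrictions, with the same content in Sections 3.1 and 6.4:

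- Criterion 18, for female subjects: "Positive highly sensitive pregnancy test at screening or admission for WOCBP".
- Criterion 21, for male subjects: "Male subjects with pregnant or lactating partners".

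Section 9.1.6 sets out the testing: "A highly sensitive urine pregnancy test will be performed at screening for all female subjects". A serum test follows at admission, and women of childbearing potential have a urine test before discharge. Criterion 23 lets the principal investigator exclude anyone for any reason.

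**The concern.** Criterion 21 shows that the authors thought about lactation when they wrote the eligibility rules. It removes a man who would receive the drug because his partner is lactating. The woman who would receive the intravenous dose herself has no matching rule. Because Section 6.1 rests women's eligibility on the listed criteria, an omission from the list decides who may enter.

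The person affected would be a nursing infant, who is not a trial subject and cannot consent. This is the first study of the agent in people, and Section 6.5 states that the human half-life is unknown. Section 6.5.3 provides for following a pregnancy and reporting on the child after delivery. Nothing comparable exists for a breastfed infant. Adverse events are defined for subjects (Section 9.10.1), and the safety population contains dosed subjects only (Section 10.1.1). An effect on an infant would therefore fall outside the planned data collection.

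**Working it through.** No calculation settles this point. The check is a reading of every place where a rule on breastfeeding could stand.

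| Place | What it covers | Breastfeeding female subject? |
|---|---|---|
| 3.1 and 6.3, inclusion criteria 1–13 | health, age, weight, laboratory tests, contraception, consent | not mentioned |
| 3.1 and 6.4, exclusion criterion 18 | positive pregnancy test | not mentioned |
| 3.1 and 6.4, exclusion criterion 21 | men with pregnant or lactating partners | male subjects only |
| 3.1 and 6.4, the other 21 exclusion criteria | medical, dietary, drug and administrative grounds | not mentioned; 23 is open discretion |
| 3.2, schedule of activities | pregnancy tests, FSH in post-menopausal women | no question or check |
| 6.1, population rationale | fetal risk, pregnancy, contraception | not mentioned |
| 6.5 to 6.5.3 | contraception, sperm and egg donation, pregnancy | not mentioned |
| 6.6, lifestyle rules | diet, exercise, alcohol, blood donation | not mentioned |
| 9.1.6 and 9.1.7 | pregnancy and FSH tests | not mentioned |
| 9.9, withdrawal reasons | includes pregnancy | not mentioned |

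Each list has 13 + 23 = 36 criteria. The number that name lactation in a female subject is 0 of 36 in the synopsis and 0 of 36 in the body. The two lists agree, so neither fills the other's gap.

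Next, take a healthy nursing woman within the age, weight and BMI limits who uses an intrauterine device.

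1. Criterion 18: her tests are negative, so it does not apply.
2. Criterion 21: it covers men only, so it does not apply.
3. Section 6.5: an intrauterine device is a listed method, so she complies.
4. Criterion 23: this is the only remaining ground. It does not name lactation, and no scheduled procedure specifically asks about it.

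She therefore meets the listed criteria, subject to the investigator's discretion.

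Then the period after dosing. Section 5.1 confines subjects from 24 hours before to 120 hours after the dose, with discharge on Day 6. Other precautions continue beyond discharge: female contraception to 37 days after dosing (30 + 7), egg and sperm donation to 97 days (90 + 7 for men), and blood donation for at least 30 days. The 7-day component stands in for five half-lives because the human half-life is unknown. For nursing, or for milk expressed during confinement, the protocol text has no rule.

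An estimate of the infant's exposure would need the fraction of drug or manganese entering milk, its time course in humans and the amount of milk taken. The documents give none of the three.

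**The case against.** **Discretion.** Every subject needs the investigator's agreement, and a medical history is taken at screening, so a nursing mother may well be noticed and excluded under criterion 23. That is likely in practice. It is still not a rule, and the sponsor did not rely on discretion for the partners of male subjects.

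**Likely exposure is low.** Confinement rules out nursing at home for the first five days after the dose. Section 4.2 reports rapid elimination of the intact chelate in rats, mice and monkeys, with 0.058 ± 0.051% of injected manganese left in rats at 7 days. Both points stand and lower the likely exposure. Neither is offered as a lactation safeguard, and human elimination is what the trial is to measure.

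**Other documents.** The consent form or Investigator's Brochure may give advice on nursing. They were not available, so the statement about missing restrictions covers the supplied protocol text only.

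**A reader might try to put a size on the hazard.** At 55 kg the planned doses are 2.0 × 55 = 110 mg to 12.0 × 55 = 660 mg of manganese, or 110/2.5 = 44 to 660/2.5 = 264 times the daily dietary figure in criterion 10. That figure is an eligibility threshold for the subject's own diet. Setting a mother's intravenous chelated dose against it says nothing about an infant. Reassurance from the rat residue (0.058% of 660 mg, about 0.38 mg) is no firmer, because it assumes that humans eliminate the agent as rats do.

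**A reader might also cite brain retention of manganese as the expected harm.** Section 9.10.12 lists it as a class concern without qualification, but Section 4.3.3 ties it to chronic overexposure and adds that the chelate was designed to stay intact. This is a single-dose study, so the documents do not show that harm for a nursing infant.

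**Conclusion.** The point holds as an asymmetry and an omission. Lactation is named for a male subject's partner and for nobody else. In the protocol text, only the discretionary criterion 23 stands between a nursing woman who is otherwise eligible and first-in-human intravenous dosing.

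A reader might infer that criteria 18 and 21 contradict each other. They do not: they concern different people, and both can be applied to every volunteer. The protocol also gives no reason for criterion 21. Reading it as a rule against secondary exposure is an inference, although the statement in Section 6.5 about exposure through ejaculate makes it plausible. Nor is the agent untested: Sections 4.2.1 and 4.3.1 describe safety pharmacology and toxicology in animals. The accurate description is that it has not yet been evaluated in humans.

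As to size, few volunteers would be affected, and the documents do not say how many. Infant exposure cannot be quantified, either as negligible or as harmful. No endpoint, analysis or escalation rule depends on this point. The conclusion rests on the eligibility, contraception and assessment sections being complete as supplied, which they appear to be. It is worth correcting because the possible exposure falls on someone outside the trial and the correction costs very little.

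**What to change.** Reconcile criteria 18 and 21 in both Section 3.1 and Section 6.4, so that the exclusion criteria explicitly address the lactation status of female subjects, consistently with the treatment of male subjects' partners. Have lactation status asked by history at screening and again at admission, where the schedule of activities already places an eligibility review.

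The cost is a short wording change in two lists and one question asked twice, which can go into the next amendment. No new test, visit or analysis is needed. The downside is the loss of a very small number of volunteers.
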